## **10.5 Handling of protocol deviations**

After all data have been verified/coded/entered into a database, a data review will be performed. The purpose of this review will be to check all protocol deviations, define the PPS, and check the quality of the data. The review will also help decide how to manage problems in the participants' data (eg, missing values, withdrawals, dropouts, and protocol deviations). Accepted deviations from theoretical time points will be described in the appropriate documents and included in the Trial Master File. After the pre-analysis review, resolution of all issues, and documentation of all decisions, the database will be locked.

## **10.6 Handling of dropouts or missing data**

Participants who withdraw from the study before receiving study medication will be replaced and will not be included in the safety or antitumor activity assessments. Safety analyses will be conducted on all participants who have received at least 1 dose of the study medication, regardless of whether they are deemed evaluable for the assessment of a dose level (ie, they receive the planned dose during Cycle 1 [2 treatment administrations]).

Any participant who is discontinued from the study before receiving all doses of UCB6114 in Cycle 1 will be deemed nonevaluable for assessment of a dose level and will be replaced unless they experience a DLT before withdrawal.

In the context of the COVID-19 pandemic, participants who miss doses due to a positive COVID-19 diagnosis or known or expected exposure may continue in the study if, in the opinion of the investigator, they are experiencing clinical benefit and it is in their best interest to continue treatment (see Section 7.1.4).

Nonevaluable participants may be replaced to ensure that at least 3 participants receive all assigned doses of therapy at each dose level/cohort, unless accrual to that cohort has stopped due to DLTs.

Further details on any imputation of missing data will be included in the SAPs for each module.

## **10.7 Planned interim analysis and data monitoring**

No formal interim analysis will be conducted during this study; however, the SMC will regularly review all the safety, tolerability, and PK data as well as any available biomarker and ADA data for the dose escalation modules (Part A, Part B, Part C).

In Part A, Part B, and Part C, at the end of each cohort, the SMC will review all available safety, PK, ADA and biomarker data prior to any dose escalation/de-escalation decision. The composition and operation of the SMC will be clearly outlined in the SMC Charter. The PK data will be summarized after each cohort, in order to support escalation to the next proposed dose level.

In Part A1, the SMC will review all the safety and tolerability of the sentinel participant in each cohort (48 hours following first UCB6114 administration). The SMC will also review available safety, tolerability, and PK data as well as any available biomarker and ADA data once 25%, 50% and 100% study participants in Part A1 have completed the required 28-day observation period.

Before starting any subsequent study part, the Sponsor will review all available safety, tolerability, PK, and PD biomarker endpoints from other final or ongoing study part.

## **10.8 Determination of sample size**

### **10.8.1 Dose escalation modules**

The number of participants likely to be enrolled in Parts A, B, and C depends on how many dose levels are needed to define the RP2D-M and the RP2D for combination therapy.

In Part A, up to 42 eligible participants will be enrolled across 5 cohorts/dose levels. This assumes that all 5 planned dose levels are evaluated, that 1 dose level is added based on emerging data, and that, on average, each cohort includes an additional participant due to drop-out/replacement and/or the modified rolling-6 design.

In Part A1, up to 32 eligible participants will be enrolled across 4 alternative dosing schedules; 8 participants per cohort is considered sufficient to protect against unacceptable level of toxicity. The probability of declaring a dose schedule (cohort) too toxic, given a toxicity rate greater than the maximum tolerable toxicity rate (33%) is approximately 90% (Mokdad et al, 2018). However, the probability is reduced to 80% when the dose optimization module is considered independent of Part A. An administrative decision to stop enrolling into Part A1 may be made by the Sponsor at any time.

In Part B and Part C, up to 27 eligible participants will be enrolled. In both parts, it is expected that up to 3 dose levels of UCB6114 will be explored in combination with the standard TFD/TPI or FOLFOX dosing regimen, respectively. However, additional dose levels may be added based on emerging data and recommendations of the SMC. In each part of the study, between 3 and 9 participants are expected to be enrolled per dose level depending on the observed toxicity/observation of DLTs. An administrative decision to stop enrolling into Part B or Part C may be made by the Sponsor at any time.

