#### **4.1.3 Part A1 – Dose optimization (alternative dosing schedules)**

Part A1 is a multicenter, non-randomized, open-label, dose optimization module of Study ONC001 to evaluate alternative dosing schedules and infusion times for UCB6114 administered as monotherapy in patients with unresectable locally advanced or metastatic colorectal cancer, gastric cancer, cancer of the gastro-esophageal junction, or pancreatic cancer.

Part A1 may commence after the fifth cohort in Part A (Cohort 5) is considered sufficiently █ by the SMC (DLT rate less than 33%). The planned dose optimization scheme for Part A1 will assess the safety and tolerability of the drug new formulation and will explore shortening of the infusion time and less frequent dosing as follows:

- Cohort 1: 2000mg Q2W (60-minute iv infusion), 28-day treatment cycle
- Cohort 2: 2000mg Q2W (30-minute iv infusion), 28-day treatment cycle
- Cohort 3: 3000mg Q3W (90-minute iv infusion), 21-day treatment cycle
- Cohort 4: 4000mg Q4W (120-minute iv infusion), 28-day treatment cycle

Details of each planned cohort are provided in [Table 6-6](#).

Up to 32 participants will be allocated 1:1:1:1 to one of the 4 cohorts, with each cohort enrolling 8 study participants including 1 sentinel participant with an observation period of 48 hours.

The enrollment of a sentinel participant in each cohort has been included as an additional risk mitigation measure to monitor infusion related reactions and other early onset treatment-related AEs. Each sentinel participant will be assessed for at least 48 hours following the first administration of UCB6114 in the first cycle and the SMC will convene before further participants within the cohort can be enrolled.

The SMC will also convene after 25%, 50% and 100% of study participants in Part A1 have completed the required 28-day observation period. If deemed necessary, an additional SMC meeting can convene after 75% of the participants have completed the required observation period. If 1 DLT, or more, (refer to Section 4.1.2.4 for the definition of DLTs) are reported for a cohort then, an ad-hoc SMC will convene to determine if the dosing schedule and study can continue as planned.

If 3 or more participants experience DLT(s) in a given cohort, no further participants will be enrolled in the cohort and the dosing schedule will be considered to be unacceptably toxic.

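### The stated 90% and 80% chances of declaring a Part A1 schedule too toxic do not follow from the protocol's 3-of-8 rule, which gives 52% at a true DLT rate of 33%

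*Protocol*

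**What the plan says.** Protocol Section 4.1.3 describes four Part A1 cohorts, "each cohort enrolling 8 study participants including 1 sentinel participant". It has one rule that ends in a finding of excess toxicity: "If 3 or more participants experience DLT(s) in a given cohort, no further participants will be enrolled in the cohort", after which "the dosing schedule will be considered to be unacceptably toxic". A softer step comes earlier. From the first DLT in a cohort, "an ad-hoc SMC will convene to determine if the dosing schedule and study can continue as planned".

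Section 10.8.1 gives the statistical case for eight per cohort. It says the "probability of declaring a dose schedule (cohort) too toxic, given a toxicity rate greater than the maximum tolerable toxicity rate (33%) is approximately 90"%, and adds: "However, the probability is reduced to 80% when the dose optimization module is considered independent of Part A". It cites a published paper on expansion cohorts. It names no DLT threshold, no particular rate above 33% and no method for using the Part A data.

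**The concern.** The two figures in Section 10.8.1 are the only quantitative support for calling eight per cohort sufficient protection against excess toxicity. They describe a decision whose rule is fixed in Section 4.1.3, so they can be checked directly. With three DLTs needed out of eight, a schedule sitting at the protocol's own limit of 33% should produce 2.64 DLTs on average (8 × 0.33). A rule that needs three cannot then be met 80% or 90% of the time.

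The check concerns the primary safety endpoint, in cohorts that use a new formulation, a shorter infusion (Cohort 2) or larger single doses (Cohorts 3 and 4). A reader who takes the figures at face value would expect a schedule above the limit to be declared too toxic in eight or nine cases out of ten.

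**Working it through.** **Inputs.** Cohort size n = 8 and threshold of at least 3 participants with a DLT (Section 4.1.3). Tolerable limit 33%, and stated probabilities of about 90%, or 80% for Part A1 alone (Section 10.8.1). Part A cohorts of up to six, with escalation allowed at no more than one DLT in six (Section 4.1.2).

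**Step 1: the stated figures under the protocol's rule.** With true DLT rate p, P(at least 3 of 8) = 1 − [(1−p)^8 + 8p(1−p)^7 + 28p²(1−p)^6]. At p = 0.33 this is 1 − (0.0406 + 0.1600 + 0.2758) = 0.524. Using p = 1/3 gives 0.532. Neither 80% nor 90% is reproduced. The like-for-like comparison is with the stand-alone 80%, a gap of about 28 points.

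**Step 2: other true rates.** The right-hand column uses P(at least 2 of 8) = 1 − [(1−p)^8 + 8p(1−p)^7].

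| True DLT rate | At least 3 of 8 | At least 2 of 8 |
|---|---|---|
| 20% | 20% | 50% |
| 25% | 32% | 63% |
| 33% | 52% | 80% |
| 35% | 57% | 83% |
| 40% | 68% | 89% |
| 45% | 78% | 94% |
| 50% | 86% | 96% |

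At 20% the terms are 0.1678, 0.3355 and 0.2936, giving 0.203 for three or more and 0.497 for two or more. At 25% they are 0.1001, 0.2670 and 0.3115, giving 0.321 and 0.633. Solving the 3-of-8 formula for 0.80 gives p = 0.462, and for 0.90 gives p = 0.538.

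**Step 3: readings that keep 3 of 8.**
- Count a schedule as caught if Part A shows at least 2 of 6 or Part A1 at least 3 of 8. At 33% this is 1 − (1 − 0.6422)(1 − 0.5236) = 0.830, not 90%.
- Average over a uniform prior on rates above 33%. This gives 90.7% for Part A1 alone, which the protocol puts at 80%, and 98.1% with the either-part rule. Conditional on Part A having passed, Part A1 gives 72.7%.

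None of these yields 80% alone together with 90% combined.

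**Step 4: thresholds that come close.** At 33%, at least 2 of 8 gives 1 − (0.0406 + 0.1600) = 0.799. Pooling six Part A participants with eight from Part A1, at least 3 of 14 gives 1 − (0.0037 + 0.0253 + 0.0811) = 0.890. That pair lies within about one point of the protocol's 80% and 90%.

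**The case against.** The best reply is that Section 10.8.1 speaks of rates above 33% and fixes none, so 52% is the least favourable point, and that the source paper is not to hand. Both are true. However, the rule still needs a rate of 46% to reach 80%, and no citation alters the binomial probability of the protocol's own rule.

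A second reply is that the rule is not the only safeguard. The committee reviews each sentinel participant, meets after 25%, 50% and 100% of participants have completed observation, and meets ad hoc after one DLT. At 33% the chance of at least one DLT in eight is about 96%. This stands: a schedule that escapes the 3-of-8 rule has not escaped review. But that review is discretionary and does not itself declare a schedule too toxic, so it cannot supply the stated probabilities.

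A third reply is that the 90% figure borrows from Part A. Part A1 opens only once Part A Cohort 5 has shown a DLT rate below 33%, so Part A adds no further detection while Part A1 runs. Nor did Part A test Cohort 2's infusion time or the larger single doses.

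Two stronger readings are tempting and not supported. From "Nonevaluable participants may be replaced to ensure that at least 3 participants receive all assigned doses of therapy at each dose level/cohort" a reader might infer that cohorts could be judged on far fewer than eight evaluable participants. The same Section 10.6 says that anyone discontinued before all Cycle 1 doses will be replaced unless a DLT came first, and Sections 6.6.1.2 and 7.1.4 require replacement when the second planned dose is missed for reasons other than toxicity. A reader might also infer that Section 4.1.3 is right and Section 10.8.1 simply miscalculated. Step 4 shows that the calculation may be sound for another threshold, and the documents do not say which was intended.

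**Conclusion.** The concern holds as a conflict between two sections. Under the 3-of-8 rule, a schedule with a true DLT rate of 35% to 45% would go undeclared in about 43% to 22% of cohorts (1 − 0.572 and 1 − 0.780). The stated figures imply 10% to 20%. At 33% the shortfall is about 28 points against the stand-alone 80%.

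This assumes eight DLT-evaluable participants per cohort, independent outcomes and a common DLT rate within the cohort. The match to 2 of 8 and 3 of 14 is an inference about where the figures came from, not something the protocol states. No formal test depends on the two figures. What is affected is the stated justification of the cohort size.

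**What to change.** Reconcile Sections 4.1.3 and 10.8.1, with the sponsor confirming which declaring rule is intended. The choice of threshold is the sponsor's. Then replace the 90%/80% sentences with the exact operating characteristics of that rule at named true DLT rates, including the false-alarm probability at acceptable rates.

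If 3 of 8 is confirmed, the text would say that the probability of declaring a schedule too toxic is 52%, 68% and 86% at true rates of 33%, 40% and 50%, and 20% at a true rate of 20%. If another rule is confirmed, the same quantities should be given for it. If Part A data are meant to contribute, state how and for which cohorts. Note that ad hoc committee review after a single DLT is an additional, discretionary safeguard outside these figures.

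If the 3-of-8 rule stays, the cost is protocol wording and a stated figure less favourable than the present one. If the sponsor confirms a different threshold, Section 4.1.3 changes too, with the trade-off shown in the table.

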### **10.8.2 Expansion modules**

Participant numbers for Parts D, E, F, and G are based primarily on pragmatic considerations rather than formal statistical power considerations. A minimum sample size of 15 participants is proposed per expansion module (may be expanded to 30 participants). This sample size will allow the safety and antitumor activity of UCB6114 to be evaluated with reasonable confidence

prior to commencement of further clinical studies. Furthermore, based on well-established statistical principles (Gehan, 1961):

- If no responses are seen in the first 15 consecutive participants enrolled, the chances of a response rate >20% are <4%.
- If no responses are seen in 30 consecutive participants enrolled, the chances of a response rate >10% is <5%.

For Parts F and G, in which UCB6114 will be evaluated in combination with another agent/regimen, response rates may be higher depending on the participant population and combination agent/regimen chosen.

Accordingly, a clinically meaningful improvement in the response rate will be defined for Parts F and G based upon the tumor type, line of therapy, and current SOC response probability. A 2-stage design (Simon, 1989) will be used to expand the cohorts should the observed response rate exceed the SOC expected response plus the clinically meaningful improvement threshold.

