**Table 3-3: Objectives and endpoints for the expansion modules in Parts D, E, F, and G**

Objectives	Endpoints
Primary	
To assess preliminary antitumor activity of UCB6114 when administered as monotherapy (Part D and Part E) or in combination with selected SOC regimens (Part F and Part G) according to relevant RECIST criteria	Antitumor activity as indicated by ORR
Secondary	
To characterize the safety profile of UCB6114 as monotherapy or in combination with selected SOC regimens	

• Incidence of TEAEs

• Severity of TEAEs

To document any antitumor activity observed with UCB6114 when administered as monotherapy or in combination with selected SOC regimens	Antitumor activity as indicated by: 

• DCR

• DOR

• PFS

• OS

Tertiary/exploratory	
To explore PD biomarkers of UCB6114 administered as monotherapy or in combination with selected SOC regimens	Change in transcriptional and protein marker levels in blood and tumor tissue by scheduled assessment
To characterize the PK of UCB6114 administered as monotherapy or in combination with selected SOC regimens	UCB6114 concentration by scheduled assessment and dose level
To evaluate the immunogenicity of UCB6114 administered as monotherapy or in combination with selected SOC regimens	ADA (anti-UCB6114 antibody) titer and sample status by scheduled assessment

ADA=antidrug antibody; DCR=disease control rate; DOR=duration of antitumor response; ORR=objective response rate; OS=overall survival; PD=pharmacodynamic(s); PFS=progression-free survival; PK=pharmacokinetic(s); RECIST=Response Evaluation Criteria in Solid Tumors; SOC=standard of care; TEAE=treatment-emergent adverse event

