**Table 4-1: Study modules for dose escalation and expansion**

Module	Module description
Part E	Expansion module to explore the safety and antitumor activity of UCB6114 as monotherapy with the RP2D-M dosing regimen in an alternative selected tumor type (tumor type 2). It is planned to evaluate 15 participants with a selected recurrent/metastatic tumor type 2 (to be decided based on emerging internal and external data). Up to 15 additional participants may be enrolled depending on the observed antitumor activity (total sample size of up to 30 participants).
Part F	Expansion module to explore the safety and antitumor activity of UCB6114 in combination with the SOC regimen tested in Part B (RP2D-T). It is planned to evaluate UCB6114 plus SOC in 15 participants with a selected recurrent/metastatic tumor type. Up to 15 additional participants may be enrolled depending on the observed antitumor activity (total sample size of up to 30 participants).
Part G	Expansion module to explore the safety and antitumor activity of UCB6114 in combination with the SOC regimen tested in Part C (RP2D-F). It is planned to evaluate 15 participants with a selected recurrent/metastatic tumor type. Up to 15 additional participants may be enrolled depending on the observed antitumor activity (total sample size of up to 30 participants).

iv=intravenous(ly); mFOLFOX6=leucovorin 400mg/m^2 on Day 1, 5-fluorouracil 400mg/m^2 on Day 1 + 1200mg/m^2/day on Day 1 and Day 2, and oxaliplatin 85mg/m^2 on Day 1; mTPI= modified toxicity probability interval; QW=once weekly; Q2W=every 2 weeks; Q3W=every 3 weeks; PD=pharmacodynamics; PK=pharmacokinetics; RP2D-F=recommended Phase 2 dose of UCB6114 when used in combination with FOLFOX; RP2D-M=recommended Phase 2 dose for monotherapy; RP2D-T=recommended Phase 2 dose of UCB6114 when used in combination with TFD/TPI; sc=subcutaneous; SOC=standard of care; TFD/TPI=trifluridine/tipiracil

In Part A, each cohort will include 3 to 6 participants. Dose escalation (or de-escalation) will be guided by safety assessments and available PK data. At each dose level, PD samples will be collected to evaluate the PK/PD relationship.

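### Parts F and G: the stage-1 expansion bar is set at the target response rate, so a regimen truly at that target would fail to expand about half the time, which does not fit the Simon design named

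*Protocol*

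**What the plan says.** Objective response rate is the primary endpoint of the expansion modules (Table 3-3: "Antitumor activity as indicated by ORR"). Section 10.8.2 gives the size: "A minimum sample size of 15 participants is proposed per expansion module (may be expanded to 30 participants"). Table 4-1 makes the second block conditional for both Part F and Part G: "Up to 15 additional participants may be enrolled depending on the observed antitumor activity (total sample size of up to 30 participants").

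For Parts F and G, section 10.8.2 adds that "a clinically meaningful improvement in the response rate will be defined for Parts F and G", depending on tumor type, line of therapy and the current standard-of-care response probability. It then names a Simon two-stage design, which "will be used to expand the cohorts should the observed response rate exceed the SOC expected response plus the clinically meaningful improvement threshold". It gives no standard-of-care rate, improvement, alpha, power or cut-offs, and describes the participant numbers as "based primarily on pragmatic considerations rather than formal statistical power considerations".

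Section 10.7 says: "No formal interim analysis will be conducted during this study".

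**The concern.** Write p0 for the standard-of-care response rate and p1 for p0 plus the clinically meaningful improvement. In a Simon design, stage 1 screens out regimens that look no better than p0. Its cut-off r1 is chosen so that a regimen truly at p1 is rarely stopped, and whether the improvement has been reached is judged on the full sample. The protocol's sentence moves that judgement to the first look by requiring the observed rate to exceed p1.

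When the true rate is p1, the observed rate falls on either side of p1 roughly equally often. Expansion of a regimen that delivers exactly the improvement the sponsor calls meaningful would then be close to a coin toss. A combination worth pursuing could be left at 15 participants for that reason alone.

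There is also a smaller point. A stage-1 decision on the primary endpoint is an interim decision, and section 10.7 says that none will be made formally anywhere in the study.

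**Working it through.** **Inputs.** Stage 1 is n1 = 15 and the maximum is n = 30 (section 10.8.2, Table 4-1). The bar is an observed rate strictly above p1 (section 10.8.2). The values of p0 and p1 are assumed, with p1 scanned from 10% to 70%. For the comparison designs, alpha of at most 0.10 (one-sided) and power of about 80% are also assumed. All probabilities are exact binomial.

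**The protocol's own figures.** The only operating characteristics in section 10.8.2 are the zero-response probabilities, and both reproduce: 0.8^15 = 3.5% (stated as below 4%) and 0.9^30 = 4.2% (stated as below 5%). None is given for the expansion rule in Parts F and G.

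**The written rule.** Expansion needs at least k = floor(15 × p1) + 1 responses. The chance of not expanding at the target is P(X ≤ k − 1), with X binomial(15, p1).

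| True rate = p1 | 15 × p1 | Responses needed | Not expanded |
|---|---|---|---|
| 20% | 3.00 | 4 | 64.8% |
| 25% | 3.75 | 4 | 46.1% |
| 30% | 4.50 | 5 | 51.5% |
| 40% | 6.00 | 7 | 61.0% |
| 50% | 7.50 | 8 | 50.0% |
| 60% | 9.00 | 10 | 59.7% |
| 65% | 9.75 | 10 | 43.6% |

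Over every whole-percent p1 from 10% to 70%, the range is 40.1% (at 13%) to 64.8% (at 20%), with a mean of 51.4%. The unevenness comes from the small number of possible response counts. If the bar is read as at least p1 instead of above it, the values at 5-point steps run from 39% to 60%.

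**What a Simon design requires.** A regimen stopped at stage 1 cannot succeed, so power of 1 − β requires P(early stop at p1) ≤ β. That is at most 20% for 80% power and 10% for 90% power. No value in the scan comes near this. For comparison, optimal Simon designs at alpha 0.10 and power 0.80 (searched up to 40 participants) have these stage-1 cut-offs r1/n1:

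- 10% vs 30%: 0/7
- 20% vs 40%: 2/12
- 30% vs 50%: 5/15
- 40% vs 60%: 5/12

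The last three cut-offs lie close to p0 and the first lies below it. Early-stop probabilities at p1 are 8% to 16%.

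**The same 15 + 15 with r1 near n1 × p0.**

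| Assumed p0 / p1 | Stop if | Succeed if | Early stop at p1 | Power | Alpha |
|---|---|---|---|---|---|
| 10% / 30% | ≤1/15 | >5/30 | 3.5% | 91% | 6.8% |
| 20% / 40% | ≤3/15 | >9/30 | 9.1% | 79% | 5.5% |
| 30% / 50% | ≤4/15 | >12/30 | 5.9% | 80% | 8.0% |
| 40% / 60% | ≤6/15 | >15/30 | 9.5% | 79% | 8.8% |

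**What the lower bar costs.** Take 20% vs 40%. The written rule needs at least 7 of 15. It expands a true 40% regimen with probability 39% and a true 20% regimen with probability 2%. A cut-off of at least 4 of 15 expands them with probability 91% and 35%.

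**The case against.** Four arguments on the other side carry weight.

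- **The parts are not yet specified.** Section 4.1 defers their characteristics to planned amendments and says that not all modules may open. Section 10.4.1 defers further description of the antitumor analysis. This lowers the urgency but does not cure the sentence. The standard-of-care rate and the improvement are deferred; the criterion that uses them is already stated as what will be done. An amendment that only filled in the two numbers would carry the bar forward.
- **The sentence is not worded as an exclusive condition.** It does not say what happens below the bar, and the Synopsis says that up to 15 more participants may be enrolled depending on emerging data. The non-expansion figures therefore hold if the sentence is applied as the go/no-go criterion. That is its natural reading, but not the only possible one.
- **No test or power is stated.** A reader might infer that Parts F and G have a fixed power ceiling equal to the chance of expanding. The documents do not support that claim. They give no alpha, power or final cut-off, call the numbers pragmatic, and plan a response proportion with a Clopper-Pearson interval (section 10.4.1.2). What can be supported is the chance of expansion.
- **A sponsor may want a strict bar in a small signal-seeking cohort.** That is legitimate, since the strict bar rarely expands an inactive regimen. It is then not a Simon stage-1 rule, and the risk at the sponsor's own target should be stated.

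On section 10.7, a reader might extend the contradiction to the 15-participant decision in Parts D and E. That decision is discretionary and tied to no named two-stage design, so it need not be a formal interim analysis.

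**Conclusion.** The point holds for the expansion criterion. Section 10.8.2 names a Simon two-stage design and gives it a stage-1 bar at p1, and the two are incompatible at conventional power. Applied at 15 participants, the bar leaves a regimen truly at the target unexpanded about half the time.

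The qualitative result does not depend on which rates are chosen later, because it holds across the whole range scanned. The exact percentage does depend on them. Some targets fall below half, so it would be wrong to say that such a regimen always fails at least half the time.

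This is a should-fix item tied to the opening of Parts F and G. Neither can open on the current text.

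**What to change.** Before or with the amendment that opens Parts F and G, replace the sentence in section 10.8.2 with a rule of this form: Parts F and G use a Simon two-stage design with p0 equal to the standard-of-care response rate and p1 equal to p0 plus the clinically meaningful improvement; stage 2 opens if stage-1 responses exceed r1; r1/n1 and r/n are derived for stated alpha and power; the improvement is judged at the end of stage 2. The 15 + 15 layout can be kept with r1 near n1 × p0, as the second table shows, although the alpha and power chosen may favor a different n1.

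If the strict bar is intended, drop the Simon reference and state the roughly 40% to 65% risk of not expanding at the target.

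In section 10.7, add a one-line exception for the Part F and G stage-1 decision. None is needed for Parts D and E.

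The maximum sample size need not rise. The cost is that more cohorts on an inactive regimen would expand: 35% instead of 2% in the example with a true rate of 20% and a target of 40%. That cost belongs to the Simon design the protocol already names.
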